5.2. Pre-Treatment Criteria

Patients presenting to Brigham and Women's Hospital who meet the eligibility criteria above will be identified by a radiation oncologist, medical oncologist, neuro oncologist, or surgical oncologist and offered participation in the study. All patients must have undergone prior MRI-based imaging of the brain, as is standard of care. Renal function will be assessed if needed (e.g. diagnosis of chronic kidney disease) per standard of care and no other pretreatment evaluations other than current standard of care testing are required.

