3 PARTICIPANT SELECTION

3.1 Eligibility Criteria

- 3.1.1. Participants must have a biopsy proven solid malignancy and at least one intracranial measurable lesion spanning ≥ 5 mm in maximal unidimensional size and radiographically consistent with or pathologically proven to be a brain metastasis AND meet one of the following additional criteria regarding the primary site or nature of the intracranial disease:
- Melanoma with intracranial growth consistent with tumor progression despite immunotherapy
 - Gastrointestinal primary
 - HER2 positive breast cancer (subtype assessed using most representative tissue available in opinion of enrolling clinician and/or study PI)
 - Cystic metastases
 - Metastases ≥ 2 cm in maximal unidimensional size
 - Locally recurrent metastases after prior stereotactic radiation
 - Locally recurrent metastases after prior whole brain radiation
- *Patients with metastases from melanoma, GI primaries, or HER2+ breast cancer, as well as those with cystic metastases or metastases ≥ 2 cm in maximal unidimensional size, who have local recurrences after prior brain-directed radiation can only be treated in the strata permitting prior radiation (last two strata above)*
- 3.1.2. Age ≥ 18 years at diagnosis of brain metastases
- 3.1.3. Estimated glomerular filtration rate of ≥ 60 mL/min/1.73m²
- 3.1.4. Karnofsky performance status of at least 70 (i.e. at minimum, “cares for self” but “unable to carry on normal activity or do active work”)
- 3.1.5. Estimated survival based on extracranial disease of at least 3 months in the opinion of the enrolling clinician and/or study PI
- 3.1.6. Ability to understand and the willingness to sign a written informed consent document
- 3.1.7. The effects of AGuIX on the developing human fetus are unknown. For this reason, women of child-bearing potential must agree to use adequate contraception prior to study entry and for the duration of the therapeutic component of study participation

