3.2 Exclusion Criteria

- 3.2.1. Participants who cannot undergo a brain MRI
- 3.2.2. Participants who cannot receive gadolinium
- 3.2.3. Participants with widespread, definitive leptomeningeal disease
- 3.2.4. Patients requiring radiation to either >10 targets (if naïve to whole brain radiation) or >20 targets (if whole brain radiation has been given previously) per the discretion of the treating clinician and/or study PI
- 3.2.5. Pregnant women are excluded from this study because of the potential deleterious effects of gadolinium on the developing fetus. Because there is an unknown but potential risk for adverse events in nursing infants, women who are breastfeeding are

- not eligible for this study
- 3.2.6. In cohorts who have received prior brain-directed radiation, patients are not eligible for this study if they have active (at the time of protocol screening) brain metastases that require radiation that are in or within 1.0cm of the brainstem, eyes, optic nerves, or optic chiasm if the juxtaposed organ at risk (i.e. brainstem, eyes, optic nerves, or optic chiasm) has previously received either >6.0 Gy in a single fraction or, if prior radiation was fractionated, a cumulative dose in 2.0 Gy equivalents, using an alpha/beta ratio of 2, of >40.0 Gy. In addition, all patients who have had prior brain-directed radiation, regardless of technique/dose/fractionation, are not eligible for the study until written approval is provided by the study/site PI.

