4 REGISTRATION AND RANDOMIZATION PROCEDURES

4.1 General Guidelines for DF/HCC Institutions

Institutions will register eligible participants in the Clinical Trials Management System (CTMS) OnCore. Registrations must occur prior to the initiation of any protocol-specific therapy or intervention. Any participant not registered to the protocol before protocol-specific therapy or intervention begins will be considered ineligible and registration will be denied.

An investigator will confirm eligibility criteria and a member of the study team will complete the protocol-specific eligibility checklist.

The eligibility checklist(s) and all pages of the consent form(s) will be faxed to the ODQ at [contact]. The ODQ will (a) review the eligibility checklist, (b) register the participant on the protocol, and (c) randomize the participant.

Randomization can only occur during ODQ business hours (8:30am - 5pm Eastern Time, Monday through Friday excluding holidays).

An email confirmation of the registration and/or randomization will be sent to a secondary clinical research coordinator (secondary CRC, the unblinded coordinator listed below) immediately following the registration and/or randomization. The patient, treating clinician, primary research coordinator, research nurse, study PI, and remainder of the study team will remain blinded to the treatment assignment. The secondary research coordinator will coordinate with the pharmacy to facilitate preparation and distribution of the study agent or placebo and then have no further role in study procedures, as discussed below. The secondary research coordinator will not interact with the patient in any way.

Following registration, participants may begin protocol-specific therapy and/or intervention. Issues that would cause treatment delays should be discussed with the study PI of the registering site.

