5.8. Radiation Plan

Radiation therapy will be given per standard of care (i.e. non-investigational) approaches as outlined here:

Physician credentialing

In order to be eligible to treat patients on this study, physicians must be credentialed for contouring and treatment planning for brain-directed stereotactic radiation. All radiation oncologists at an institution participating in the study may enroll patients, but patients cannot be treated until the treating physician is credentialed. The credentialing process will entail a review of the contours and radiation plan for the first enrolled case, prior to treatment, by the study PI. If no significant edits to the contours are indicated and if all planning criteria listed below are met the treating physician will be credentialed and can treat future patients without pre-treatment review. Contours/plans which require significant adjustments by the study PI must be edited prior to treatment initiation; in such cases, the physician seeking credentialing will be provided with feedback and must submit a contour/plan for review prior to treatment of the next patient enrolled.

Timing of radiation

Stereotactic radiation must begin within 21 days after registration and within 14 days of the MRI

used for radiation planning. Patients cannot receive concurrent systemic chemotherapy with radiation. A minimum of five days is required between last administration of chemotherapy and initiation of radiation. A minimum of three days is required between last administration of radiation and initiation of post-radiation chemotherapy. Radiation must be delivered at an enrolling center; stereotactic radiation at outside centers will not be permitted.

Radiation dose

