Lesions <2 cm in maximum diameter will be treated with stereotactic radiosurgery (SRS), generally 20 Gy in 1 fraction. Lesions between 2.0 and 2.5-3.0 cm in maximum diameter will generally be treated to 18 Gy in 1 fraction. The volume receiving 12 Gy (V12) should be limited to <10cc; dose reductions are acceptable if the V12 constraint cannot be met via replanning, with a minimum dose of 16 Gy. Lesions >2.5-3 cm will generally be treated with stereotactic radiotherapy (SRT) to 30 Gy in 5 fractions given on consecutive weekdays. Surgical cavities can be treated to 15-20 Gy in one fraction (based on size and V12 criteria above) or, for medium sized cavities (as defined above and below), either 30 Gy in 5 fractions (gross residual/recurrent disease present) or 25 Gy in 5 fractions (no gross residual/recurrent disease present) on consecutive weekdays will be employed. Targets >4-5cm in maximal unidimensional size can be dose reduced to 23-29 Gy in 5 fractions, at the discretion of the treating clinician and/or study PI; in surgically naïve metastases >4-5cm in size, utilization of resection prior to radiation is strongly encouraged. If a metastasis that would be treated normally with SRS is adjacent to a metastasis that must receive SRT (so that a significant degree of scatter dose from the SRT field will include the potential SRS field) it is acceptable for the treating investigator to treat both metastases with SRT. Patients who have received prior radiation which deposited scatter dose to a current intracranial target (e.g. prior head and neck radiation) may have dose / fractionation adjustments at the discretion of the treating clinician and study PI. For patients requiring both SRS and SRT, treatment can be over 5 or 6 days based on whether SRS is administered concurrently or sequentially with SRT (as determined by the treating clinician and/or study PI).

Physical factors

Treatment will be delivered using megavoltage machines with photon beams.

Simulation, immobilization, and localization

The patient will be treated in the supine position. A tightly fitting thermoplastic mask will be employed for immobilization. A CT simulation will be performed, with a maximum slice thickness of 1.5mm.

Treatment planning and patient setup

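### Every participant must have an eGFR of at least 60, but section 5.2 makes renal assessment conditional and nothing limits the age of an acceptable result

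*Protocol*

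**What the plan says.** Protocol section 3.1.3 lists, without exception, "Estimated glomerular filtration rate of ≥ 60" mL/min/1.73m² as an inclusion criterion.

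Protocol section 5.2 addresses patients "who meet the eligibility criteria above" and then states: "Renal function will be assessed if needed (e.g. diagnosis of chronic kidney disease) per standard of care and no other pretreatment evaluations" beyond current standard-of-care testing are required.

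Protocol section 4.1 describes the check before randomization: "An investigator will confirm eligibility criteria and a member of the study team will complete the protocol-specific eligibility checklist". It continues: "The ODQ will (a) review the eligibility checklist, (b) register the participant on the protocol, and (c) randomize the participant".

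Protocol section 3.2.2 separately excludes "Participants who cannot receive gadolinium".

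The three calendars in Protocol section 10 carry a 21-day footnote on the baseline column. None has a row for creatinine, eGFR or any other laboratory test, at baseline or later.

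**The concern.** A numeric floor that applies to everyone can be verified only from a measured value. Section 5.2 ties the measurement to need, and its example is a patient already known to have chronic kidney disease. Those patients, and the ones excluded under section 3.2.2, have a problem that is already recognised. A floor for all participants adds protection mainly for reduced function that is undiagnosed, or that has developed since the last test. For those patients the conditional clause gives no prompt to test.

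The agent makes this matter. Section 2.3 says AGuIX is small enough to be cleared by the kidneys. Section 5.1 gives 100 mg/kg twice with radiosurgery alone and three times when fractionated stereotactic radiotherapy is used. Section 7.1 says that the incidence of renal failure has not been assessed, because the renal data are extrapolated from animals. It also lists nephrogenic systemic fibrosis, at undetermined frequency, for the reference gadolinium agent.

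What is at stake is participant safety and the verification of eligibility. No effect on the primary analysis is claimed; section 13.7.2 makes it intent-to-treat.

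**Working it through.** The plan gives no figure to reproduce. The check is whether any part of the protocol supplies what section 3.1.3 needs: a renal value for each participant, recent enough to describe that participant at treatment.

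1. **Criterion (3.1.3).** Universal and numeric. No date or window is attached to the value.
2. **Pre-treatment testing (5.2).** Conditional. Chronic kidney disease is an example and not the only trigger, so a clinician may test others, but nothing requires it.
3. **Registration (4.1).** The investigator's confirmation and the central checklist review both come before randomization. A blank eGFR entry would probably be caught. No renal test is named and no maximum age is given, so this section offers no stated ground for rejecting an old result.
4. **Exclusions (3.2).** Section 3.2.2 works only where the inability to receive gadolinium is already known.
5. **Calendars (section 10).** The 21-day baseline footnote applies to the listed items. With no renal row, it covers no renal test.
6. **After entry.** The modification table in section 6 covers neurologic toxicity only, and no renal laboratory test is scheduled between infusions or in follow-up. Reduced function missed at entry would not be found by any scheduled test before the second or third dose.

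Planned exposure, from section 5.1:

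- radiosurgery alone: 2 × 100 = 200 mg/kg
- fractionated radiotherapy, with or without radiosurgery: 3 × 100 = 300 mg/kg

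For context, the rat study in section 7.1 used two injections at a human-equivalent dose of 121 mg/kg, or 2 × 121 = 242 mg/kg in total. It found minimal tubular vacuolation that reversed after a 10-week recovery period. The fractionated schedule exceeds that total, although each single dose is lower. This is not a safety margin; it shows only why renal function at entry deserves a firm rule.

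**Result.** Steps 1 and 2 do not match: a universal criterion is paired with a conditional test. Steps 3 to 6 do not close the gap for a value that exists but is old, or for function presumed normal because no kidney disease is known.

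**Size.** The protocol does not say how often standard care supplies a recent creatinine, so the number of affected participants cannot be derived. Section 13.2 expects about 67 patients in the AGuIX arm. That is everyone who would receive the agent, not a count of those without a recent value.

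**The case against.** The strongest reply is that the sections can be read together. Section 3.1.3 is unconditional. Section 5.2 speaks of patients who already meet the criteria and says only when a new test must be ordered. Section 4.1 has an investigator confirm eligibility and a central office review the checklist before randomizing. This part stands. A reader might infer that section 5.2 waives section 3.1.3, or that patients may be randomized with no eGFR at all. The protocol does not support either reading: enrolling such a patient would breach section 3.1.3 and require a checklist item to be confirmed without evidence.

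It can also be said that the checklist may set a date window. The checklist is not reproduced in the protocol, so this cannot be excluded. But section 5.2 as written gives the checklist no window to enforce, and its wording points the other way.

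Finally, the documented renal risk is limited. Section 2.3 reports no significant acute renal toxicity in the 15-patient phase I study, at doses up to 100 mg/kg, and many patients will have a recent creatinine from routine care. Both points keep the practical risk low. Neither replaces verification of a criterion that this protocol sets for itself, and the protocol does not say that routine care supplies the value.

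**Conclusion.** The point holds in a limited form. Section 5.2 makes conditional the assessment on which a universal safety criterion depends, and no section or calendar schedules a renal test or limits the age of an acceptable result. The main exposure is a patient without known kidney disease who is accepted on an old value or on presumed normal function.

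The change is worth making because this is a safety criterion and the remedy is cheap. The number affected cannot be estimated and the practical risk is probably small. The conclusion assumes that the checklist sets no window of its own; if it does, the remaining fault is that section 5.2 is worded inconsistently with it.

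**What to change.** In Protocol section 5.2, replace the conditional clause on renal function with: *An eGFR obtained within 21 days before registration must be on file for every participant before randomization; a standard-of-care result is acceptable.* Add a matching baseline row to the three calendars in section 10. Leave the threshold in section 3.1.3 as it is.

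The 21 days follow the existing baseline footnote and are a judgement. The rule limits the age of the result at registration, not at each infusion: section 5.8 says "Stereotactic radiation must begin within 21 days after registration", and section 6 allows holds for grade 3 neurologic toxicity. A team wanting closer control could tie the window to the first infusion instead.

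The cost is one sentence, three calendar rows, and an occasional routine creatinine test for a patient with no result in the window. Where routine care already provides one, nothing changes.

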5.3. Agent Administration

AGuIX is a Gadolinium-chelated polysiloxane based nanoparticle. Its chemical formula is $(\text{GdSi}_{13-8}\text{C}_{24-34}\text{N}_{5-8}\text{O}_{15-30}\text{H}_{40-60}, n\text{H}_2\text{O})_x$. Its pharmaceutical form is sterile lyophilized powder (1000 mg of AGuIX/vial). Reconstitution of the solution is utilized with 10.00mL of sterile water for injectable preparation concentration for a final AGuIX concentration of 100 mg/mL. The pH of the final solution is then 7.3 +/- 0.3. AGuIX should be administered as a continuous intravenous infusion using a rate-regulating device per institutional guidelines with associated pre-medications. It should not be administered as an IV push. It should be administered at a dose rate of 2 mL/min. Vials contain no preservative and are suitable for single use only. No intravenous prehydration is required.

5.4. General Concomitant Medication and Supportive Care Guidelines

Women of childbearing potential and men must agree to use adequate contraception (examples include condom, intrauterine device (IUD), oral contraceptive, double-barrier method, etc.), for the duration of study participation.

5.5. Criteria for Taking a Participant Off Protocol Therapy

Treatment will continue until one of the following criteria applies:

- Intercurrent illness that prevents further administration of treatment
- Unacceptable adverse event(s)
- Participant demonstrates an inability or unwillingness to comply with the infusion regimen and/or documentation requirements
- Participant decides to withdraw from the protocol therapy
- General or specific changes in the participant's condition render the participant unacceptable for further treatment in the judgment of the treating investigator

Participants will be removed from the protocol therapy when any of these criteria apply. The reason for removal from protocol therapy, and the date the participant was removed, must be

documented in the case report form (CRF). Alternative care options will be discussed with the participant.

When a participant is removed from protocol therapy and/or is off of the study, the participant's status must be updated in OnCore in accordance with [REGIST-OP-1](#).

5.6. Duration of Follow Up

Participants will be followed until death or censoring/withdrawal from the protocol. Participants removed from protocol therapy for unacceptable adverse event(s) will be followed until resolution or stabilization of the adverse event.

5.7. Criteria for Taking a Participant Off Study

Participants will be removed from the study when any of the following criteria apply:

- Lost to follow-up despite three attempted contacts from members of the study team
- Withdrawal of consent for data submission
- Death

The reason for taking a participant off study, and the date the participant was removed, must be documented in the case report form (CRF). In addition, the study team will ensure the participant's status is updated in OnCore in accordance with [REGIST-OP-1](#).

5.8. Radiation Plan

Radiation therapy will be given per standard of care (i.e. non-investigational) approaches as outlined here:

Physician credentialing

In order to be eligible to treat patients on this study, physicians must be credentialed for contouring and treatment planning for brain-directed stereotactic radiation. All radiation oncologists at an institution participating in the study may enroll patients, but patients cannot be treated until the treating physician is credentialed. The credentialing process will entail a review of the contours and radiation plan for the first enrolled case, prior to treatment, by the study PI. If no significant edits to the contours are indicated and if all planning criteria listed below are met the treating physician will be credentialed and can treat future patients without pre-treatment review. Contours/plans which require significant adjustments by the study PI must be edited prior to treatment initiation; in such cases, the physician seeking credentialing will be provided with feedback and must submit a contour/plan for review prior to treatment of the next patient enrolled.

Timing of radiation

Stereotactic radiation must begin within 21 days after registration and within 14 days of the MRI

used for radiation planning. Patients cannot receive concurrent systemic chemotherapy with radiation. A minimum of five days is required between last administration of chemotherapy and initiation of radiation. A minimum of three days is required between last administration of radiation and initiation of post-radiation chemotherapy. Radiation must be delivered at an enrolling center; stereotactic radiation at outside centers will not be permitted.

Radiation dose

Lesions <2 cm in maximum diameter will be treated with stereotactic radiosurgery (SRS), generally 20 Gy in 1 fraction. Lesions between 2.0 and 2.5-3.0 cm in maximum diameter will generally be treated to 18 Gy in 1 fraction. The volume receiving 12 Gy (V12) should be limited to <10cc; dose reductions are acceptable if the V12 constraint cannot be met via replanning, with a minimum dose of 16 Gy. Lesions >2.5-3 cm will generally be treated with stereotactic radiotherapy (SRT) to 30 Gy in 5 fractions given on consecutive weekdays. Surgical cavities can be treated to 15-20 Gy in one fraction (based on size and V12 criteria above) or, for medium sized cavities (as defined above and below), either 30 Gy in 5 fractions (gross residual/recurrent disease present) or 25 Gy in 5 fractions (no gross residual/recurrent disease present) on consecutive weekdays will be employed. Targets >4-5cm in maximal unidimensional size can be dose reduced to 23-29 Gy in 5 fractions, at the discretion of the treating clinician and/or study PI; in surgically naïve metastases >4-5cm in size, utilization of resection prior to radiation is strongly encouraged. If a metastasis that would be treated normally with SRS is adjacent to a metastasis that must receive SRT (so that a significant degree of scatter dose from the SRT field will include the potential SRS field) it is acceptable for the treating investigator to treat both metastases with SRT. Patients who have received prior radiation which deposited scatter dose to a current intracranial target (e.g. prior head and neck radiation) may have dose / fractionation adjustments at the discretion of the treating clinician and study PI. For patients requiring both SRS and SRT, treatment can be over 5 or 6 days based on whether SRS is administered concurrently or sequentially with SRT (as determined by the treating clinician and/or study PI).

Physical factors

Treatment will be delivered using megavoltage machines with photon beams.

Simulation, immobilization, and localization

The patient will be treated in the supine position. A tightly fitting thermoplastic mask will be employed for immobilization. A CT simulation will be performed, with a maximum slice thickness of 1.5mm.

Treatment planning and patient setup

The GTV will cover the metastasis (or cavity plus any residual tumor in patients who have had neurosurgical resection) as identified by contrast enhanced MRI and CT (contrast optional) obtained within 14 days of the treatment initiation date. The MRI must be obtained with a T1 post contrast sequence with a maximal slice thickness of 1.5 mm (e.g. magnetization prepared rapid gradient echo (MPRAGE), spoiled gradient (SPGR) sequences or equivalent). Contouring

software capable of 3D reformatting is required. No CTV is to be used. The PTV will be 1mm for intact lesions and 2mm for cavities. For patients who have rapidly growing gross disease an extra 0.1-1mm of PTV margin can be added at the discretion of the treating clinician to account for growth between planning and treatment; in such cases the time between planning and treatment should be minimized to the greatest extent possible. Treatments will be delivered through volumetric modulated arc therapy (VMAT) for PTV volumes >1.0 cm in maximum diameter. For PTV volumes with a maximum dimension of 0-1.0 cm in diameter either VMAT, circular collimators, or multiple static fields will be acceptable. More than one isocenter can be used if deemed as indicated by the treating physician and/or study PI. The prescription will generally be normalized to the 60-95% isodose line but alternative normalizations (e.g. using a lower normalization to maximize dose fall off) can be utilized by the treating physician and/or study PI if deemed appropriate. Regarding coverage metrics, 100% of the GTV should be covered by the prescription dose. At least 99% (ideal) / 98% (at minimum) of the PTV should be covered by the prescription isodose line. The entire PTV should be covered by 90% (ideal) / 85% (at minimum) of the prescription dose. Daily set up with cone beam CT or stereoscopic KV imaging and use of a couch capable of making linear and rotational corrections is mandated. Use of real-time motion management with 3-dimensional surface monitoring is optional but encouraged.

Critical Structures

Dose constraints for stereotactic radiosurgery to critical structures will be as follows:

Dose constraints for stereotactic radiosurgery*

Organ at Risk	Tolerance	Dose Modification Regimen
Eyes, Optic Nerves, Optic Chiasm	Point dose ≤ 8 Gy	If point dose > 8 Gy, undercover PTV while maintaining 100% GTV coverage. If not achievable, dose reduce GTV to highest dose which meets optic constraint, through 16 Gy. If 100% of GTV cannot be safely covered by 16 Gy, then an acceptable variation will be to convert to stereotactic radiotherapy – see Table below
Brainstem (defined as brainstem volume, inclusive of upper spinal cord, minus GTV)	Dose to 0.035cc ≤ 12 Gy	If dose to 0.035cc > 12 Gy, undercover PTV while maintaining 100% GTV coverage. If not achievable, dose reduce GTV to highest dose which meets brainstem constraint, through 16 Gy. If 100% of GTV cannot be safely covered by 16 Gy, then an acceptable variation will be to convert to stereotactic radiotherapy – see Table below
Volume of normal brain (less the GTV) receiving > 12 Gy (per individual lesion, called the V12)	≤ 10 cc	If the V12 is > 10 cc on a per-metastasis basis, undercover PTV while maintaining 100% GTV coverage. If not achievable, dose reduce GTV to highest dose which meets constraint, through 16 Gy. If 100% of GTV

		cannot be safely covered by 16 Gy, then an acceptable variation will be to convert to stereotactic radiotherapy – see Table below
Normal brain less the GTV (for entire brain)	Mean <5-6 Gy	Administer stereotactic radiation on two or more consecutive weekdays rather than a single day (such cases must be discussed with the study PI)

*inclusive of 20% of stereotactic radiotherapy dose contribution (i.e. 1 of 5 days) if stereotactic radiosurgery and stereotactic radiotherapy are given on the same day; normal tissue constraints pertain only to the radiotherapeutic treatment course delivered on protocol.

Dose constraints for stereotactic radiotherapy to critical structures will be as follows:

Dose constraints for stereotactic radiotherapy (5 fractions)*

Organ at Risk	Tolerance	Dose Modification Regimen
Eyes, Optic Nerves, Optic Chiasm	Point dose of 25	If point dose >25 Gy undercover PTV while maintaining 100% GTV coverage. If not achievable, dose reduce GTV to highest dose which meets constraint, through 23 Gy in 5 fractions. 100% of GTV should always receive at least 23 Gy in such a scenario.
Brainstem (defined as brainstem volume, inclusive of upper spinal cord, minus GTV)	Dose to 0.035cc ≤28 Gy	If dose to 0.035cc >28 Gy, undercover PTV while maintaining 100% GTV coverage. If not achievable, dose reduce GTV to highest dose which meets brainstem constraint, through 23 Gy in 5 fractions. 100% of GTV should always receive at least 23 Gy in such a scenario.

*Inclusive of dose imparted by stereotactic radiosurgery if patient received stereotactic radiosurgery and stereotactic radiotherapy; normal tissue constraints pertain only to the radiotherapeutic treatment course delivered on protocol.

Management of radiation dose to the patient from daily localization

Cone beam CT or stereoscopic KV imaging will be used in this study. The doses used for daily localization images are extremely low. MV imaging (which deposits a markedly greater radiation dose) will not be employed in this study.

Future radiation considerations

For patients with progressive intracranial disease (e.g. local recurrence, distant intracranial failure), stereotactic radiation approaches will be favored over whole brain radiation. In settings of leptomeningeal disease or overwhelming distant intracranial failure with lack of viable systemic therapy, whole brain radiation will be considered/utilized.

